Teachers	Participate in Normative Survey (all 3 schools)
	Participate in Interviews to Refine Posters (school #1 – refinement school, exclusion of schools #2 and 3 to avoid contamination)
	Receive Lunch and Learn Teacher Training (school #2 – intervention school; school #3 as wait list control)
	Receive Teacher Workbook Guiding Student Intercept Activities) (school #2 – intervention school; school #3 as wait list control). Team provides ongoing technical assistance to help teachers engage in activities around the campaign.

Step 1: Engaging Stakeholders: As a school community-level change strategy, the goal of the proposed social norms marketing poster campaign is to change community mind-set. Given the widespread reach of misperceived norms, some key stakeholders in a community may display resistance to the approach. Therefore, the

first step in implementation is to educate key stakeholders about the model, and the plan for implementation. Stakeholder resistance will be addressed prior to the implementation of the campaign through stakeholder meetings with school administrators and teachers. A school champion (e.g., principal, teacher, counselor) will also be nominated to coordinate the campaign and engage other teachers in the initiative.

Step 2: Identifying Misperceptions: Individual communities may hold a range of false beliefs relating to HIV and STI risk, sexual risk behaviors, dating relationships, and sexual violence. Student and teacher participation in a normative school survey of perceived norms around these behaviors will identify core misperceptions in community norms within schools. To increase the credibility of the survey, it is essential that the survey have reach. As such, we aim to include a minimum of 75% of the target intervention school community.

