For the student survey, we will recruit student peers by visiting all classrooms, briefly explaining the purpose of the anonymous survey. Then we will follow the subsequent consent and assent process, which we have given careful consideration based on our own research of the most appropriate consent procedures for low-risk research with adolescents in school settings.⁷¹ Our team will visit classrooms to describe the survey to students. We will provide parents/legal guardians a letter about the nature of the research and a consent form seeking their permission for their child's participation (Appendix E), and we will provide a period of 1-2 weeks to return the form which includes our teams' contact details to answer questions and concerns. Then we revisit high school classes 1-2 weeks later. For adolescents with parental consent forms, we will verify eligibility for adolescent surveys. Inclusion criteria include: (1) adolescents attending the high school. We include adolescents attending the school regardless of gender and age (anticipating a range of 12-19 years) to get a full assessment of social ecology (rather than just focusing on the target group of the intervention, males aged 15-17 years). Interested and eligible adolescents go through assent procedures using a consent form (Appendix F). Then we provide a brief survey assessing: (1) IPV and HIV behavior data (students only); (2) predicted prevalence of IPV and sexual behaviors in their school; (3) norms and attitudes around sex, HIV, gender, and IPV.

Reimbursement. For the brief school social ecology climate survey, students and teachers will receive a small token (e.g., keychain, stationary) as appreciation.

Analysis. We will check all forms for missing data in field and during entry. We will examine key variables for skewness, variability, missing data, and outliers, with transformations to achieve normality if needed. We will conduct chi-square, Fisher's exact and t-tests to examine associations between participant demographic characteristics, social norms, and actual or predicted IPV behaviors. We look for differences between perceived norms and actual norms/behaviors. Findings inform social norms messages for the campaign.

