survey. Then we will follow the subsequent consent and assent process, which we have given careful consideration based on our own research of the most appropriate consent procedures for low-risk research with adolescents in school settings.⁷¹ Our team will visit classrooms to describe the survey to students, explaining parents/legal guardians need to indicate in writing whether they do not want their child to participate. We will provide parents/legal guardians a letter about the nature of the research seeking their permission for their child's participation, and provide a period of 1-2 weeks to return the form with our teams contact details to answer questions and concerns. Then we revisit high school classes 1-2 weeks later. For adolescents with consent forms, we will verify eligibility for adolescent surveys. Inclusion criteria include: (1) adolescents attending the high school. We include adolescents attending the school regardless of gender and age (anticipating a range of 12-19 years) to get a full assessment of social ecology (rather than just focusing on the target group of the intervention, males aged 15-17 years). Interested and eligible adolescents go through assent procedures of if 18 years and older, consent procedures. Adolescents under 18 years of age are excluded if parental consent and adolescent assent are not obtained. Then we provide a brief school social ecology climate survey assessing: (1) IPV and HIV behavior data (students only); (2) predicted prevalence of IPV and sexual behaviors in their school; (3) norms and attitudes around sex, HIV, gender, and IPV. **Retention of students** for follow-up does not apply for this one-time cross-sectional survey.

Aim 2: Qualitative Interview and Focus Groups

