For Aim 1 with adolescents, our team will visit classrooms to describe the survey to students, explaining parents/legal guardians need to indicate in writing whether they do not want their child to participate. For potential participants under 18 years of age, we will provide parents/legal guardians a letter about the nature of the research seeking their permission for their child's participation, and provide a period of 1-2 weeks to return the form with our teams contact details to answer questions and concerns. Then we revisit high school classes 1-2 weeks later. For adolescents with consent forms, we will verify eligibility for adolescent surveys. For Aim 1 for teachers interested in participation, our team will screen for eligibility and then proceed with the consent process. Study staff will provide a signed written informed consent form from each teacher who is eligible and interested in participating for them to review and then complete the survey.

For Aim 2 with teachers interested in participation, our team will then proceed with the consent process. Study staff will provide a signed written informed consent form from each teacher who is eligible and interested in participating for them to review and then schedule an interview time. For Aim 2 with adolescents, we will recruit a convenience sample of any gender, age, and race of adolescents through flyers providing contact details for study staff in the school setting and recruit in-person with permission of the school principal and teachers. All interested adolescents under 18 years of age will be sent home with written parental consent and adolescent assent forms. Parents/legal guardians will have a chance to ask questions or discuss concerns using the contact details provided to them via study information sheet and consent form. For adolescents who return signed consent forms, study staff will assess eligibility for adolescent focus groups.

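### Aim 1 student survey: the classroom message is worded as opt-out while admission is opt-in, so some willing families may return no form and coverage may fall or become selective

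*Combined protocol and SAP*

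**What the plan says.** The Aim 1 student survey procedure is described in three places.

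- **Specific Aim 1, Survey of Social Ecology.** Parents receive a letter and "a consent form seeking their permission for their child's participation", with 1-2 weeks to return it. Staff then revisit the classes: "For adolescents with parental consent forms, we will verify eligibility for adolescent surveys". This account is opt-in throughout.
- **Recruitment and retention plan, Aim 1.** At the classroom visit staff describe the survey to students and explain that "parents/legal guardians need to indicate in writing whether they do not want their child to participate". Parents then get "a letter about the nature of the research seeking their permission for their child's participation" and 1-2 weeks to return the form. After that: "For adolescents with consent forms, we will verify eligibility for adolescent surveys". The paragraph adds: "Adolescents under 18 years of age are excluded if parental consent and adolescent assent are not obtained".
- **Adequacy of Protection Against Risks, a. Informed Consent and Assent, Aim 1.** This has the same classroom sentence, the same kind of letter and return window, and the same step limited to students with consent forms. It does not have the explicit exclusion sentence.

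On coverage, Step 2 of the intervention overview treats reach as essential to the survey's credibility and says "we aim to include a minimum of 75% of the target intervention school community". The Survey of Social Ecology text aims for 75% of teachers and students and estimates 1500 students across three schools.

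**The concern.** The sentence spoken in class asks for something in writing from parents who object. The admission rule asks for something in writing from parents who agree. Both instructions stand in the same paragraph in two sections. A student who relays the classroom message at home may lead a willing parent to conclude that no reply is needed, and under the admission rule that child is then left out.

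The survey is not background data. Step 3 of the intervention overview uses it to decide which norms clear the endorsement threshold of more than 75%. Step 5 has the posters describe the survey methods so that readers accept that the figures come from most of the school. Lost forms would reduce coverage. If families who return forms differ from those who do not, the norms printed on the posters would also be selective.

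**Working it through.** **Step 1: the three accounts side by side**

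| Element | Specific Aim 1 | Recruitment plan | Informed Consent and Assent |
|---|---|---|---|
| Classroom message that parents write if they do not want participation | absent | present | present |
| Parents asked for permission, form to return in 1-2 weeks | yes | yes | yes |
| Only students with consent forms go forward | yes | yes | yes |
| Explicit exclusion of under-18s without parental consent | not stated | yes | not stated |

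The first row conflicts with the other three. The Aim 2 and Aim 3 procedures do not contain the classroom sentence, so the conflict is confined to Aim 1.

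**Step 2: can the plan's own figure be reproduced?** No. The documents give no enrolment, so 1500 can be read in two ways. If 1500 is the 75%, enrolment is 1500 / 0.75 = 2000. If 1500 is the enrolment, the aim is 0.75 × 1500 = 1125 students.

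**Step 3: how coverage depends on form return.** Let s be the share of students under 18, a the rate of assent and attendance, and r the share of minors whose form comes back. Students aged 18-19 need no parental form. Then

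coverage = a × [(1 − s) + s × r], so the return needed for 75% is r = (0.75/a − (1 − s)) / s.

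The documents give none of s, a or r. With assumed s = 0.80-1.00 and a = 0.85-1.00:

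- s = 0.80, a = 1.00: r = (0.75 − 0.20) / 0.80 = 0.688 (lowest)
- s = 0.90, a = 0.95: r = (0.789 − 0.10) / 0.90 = 0.766
- s = 1.00, a = 1.00: r = 0.750
- s = 1.00, a = 0.85: r = 0.882 (highest)

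So 75% coverage needs forms from roughly 69% to 88% of minors. Each 10-point fall in return costs 10 × a × s points of coverage, from 10 × 0.85 × 0.80 = 6.8 to 10 × 1.00 × 1.00 = 10.

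**Step 4: the part due to the sentence.** Step 3 describes any opt-in scheme, including the corrected one. If w is the share of minors whose willing parents stay silent because of the classroom wording, the loss in coverage is a × s × w. Nothing in the documents fixes w, and it could be close to zero. The direction of the effect is clear, but its size cannot be computed.

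**The case against.** The strongest reply is that families are not left with an opt-out message alone. The sentence is spoken to students. Parents receive a letter asking for permission and a form to return, and a parent reading that letter would probably reply. The sentence does not say that parents write only to refuse, and it can be read as asking for a written answer either way. The parental form is an appendix outside the reviewed text, and no classroom script is shown, so the exact words families will see are unknown. The 75% is stated as an aim; the word minimum appears once, for the target intervention school community.

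All of this is fair, and it limits the likely size. It does not remove the conflict. The admission rule tells staff whom to admit; it does not change what students are told to carry home. None of the three sections provides for telling families what an unreturned form means.

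A reader might also infer that staff could take silence as permission and survey minors without parental consent. The documents do not support that. All three accounts go forward only with students who have consent forms, the recruitment plan excludes under-18s without parental consent, and the protocol says IRB approval will be sought for all procedures.

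**Conclusion.** The point holds as an inconsistency in the consent procedure for minors. The classroom sentence in two sections does not match the opt-in rule in all three. The consequence is conditional: some willing families may return no form, their children would then be excluded, and coverage could be lower or more selective than intended.

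It would go too far to conclude that the 75% aim will be missed. The documents state no return rate or enrolment, and no share of non-return can be attributed to this sentence. The 69% to 88% range rests on assumed values of s and a. It shows only that the aim needs a high return of forms, which is reason enough not to discourage returns by the wording. Students aged 18-19 are unaffected. The correction is worth making because it is specific and costs almost nothing.

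**What to change.** In the Recruitment and retention plan (Aim 1) and in the Informed Consent and Assent section (Aim 1), and in the classroom script, replace the opt-out sentence. The new wording should match the Specific Aim 1 text and the recruitment plan's own exclusion rule: students are told that a parental consent form must be returned for anyone under 18, and that a student under 18 whose form is not returned will not be surveyed. This adds no new policy.

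Cost: two sentences of protocol text, the classroom script and an IRB notification. No analysis or sample-size text changes.

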Step 6: Addressing Criticism (a.k.a. "Kick-Back"). Given that social norms marketing attempts to change community culture, it is vital to plan for "kick-back" from the community. Addressing issues relating to the believability of the social norms marketing campaign requires having someone within the community who is trained to facilitate conversations about these issues. Towards this goal, the school randomized to receive the campaign (school #2) will have study staff involved in conducting intercept activities with students (modeling this for teachers will support teachers in their own intercept activities) to monitor believability and "kick-back" to the campaign. Intercept activities will take place during 3 visits, facilitated by our team. In the first visit, intercept activities address: 1) whether students/teachers see the message; 2) whether students/teachers believe the message; and 3) whether students/teachers think their friends/colleagues believe the message. If the messaging is not deemed credible, follow-up questions will ascertain why not. In cases where messaging is not believed, the study staff will challenge the source of disbelief using techniques developed by [name] and [name] in similar campaigns. Prior work in this area suggests that messages are sometimes not believed because teachers are making negative comments about a campaign, or because students believe that their peers were not honest in their survey responses. Students may also utilize extreme examples of behavior (i.e., graffiti, newsworthy events) to discredit the campaign. In these cases, opportunities for teacher training can be provided, interoffice messages can be sent to teachers, and classroom discussions can be implemented to educate students on how the most visible behavior (although most extreme) is not typically the norm. Study consultant [name] will be available throughout the study to consult with the study staff in developing and implementing strategies for assessing and addressing "kick-back". In the second visit, intercept activities will address: 1) whether students/teachers have talked about the message with their peers/colleagues/students; 2) whether students/teachers had challenges in that discussion and how to overcome those challenges. In the third visit, intercept activities

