Overview of Randomized Pilot Trial. We will recruit N=282 male adolescents who are the primary targets of the school community-level intervention. We will also recruit N=80 teachers (numbers are average estimates of 40 teachers/school), randomly selecting from a full list of teachers from the school. Data from this pilot trial will help prepare us for a future R01 full-scale efficacy trial that will take the form of a cluster randomized controlled trial where schools will be randomized to an intervention or control arm. In this trial, we will pilot in two schools (School #2 will receive the experimental intervention, and School #3 will serve as a wait-list control). The assignment to the experimental intervention will be randomly determined. For future trial feasibility, the first set of assessments will reflect the outcome questionnaire used at baseline, 1- and 6-months for N=282 boys (Appendix L); we also gather baseline outcomes from N=80 teachers (prior to Teacher Lunch and Learn sessions) and at post-intervention (end of the school year). The teacher instrument is in Appendix M. We will track recruitment and retention strategies and success rates. A second set of assessments for future trial feasibility will evaluate fidelity, ranking integrity and competency of our team's delivery of Teacher Lunch and Learn, Student Intercept activities in real time. These fidelity assessments follow recommendations issued by the Treatment Fidelity Workgroup of the NIH Behavior Change Consortium to ensure rigorous coding of fidelity based on a standardized monitoring checklist (Appendix N).⁷⁶ For acceptability data, we will gather intervention satisfaction forms from male adolescents (Appendix O) and teachers (Appendix P) randomized to the intervention, and gather opinions on content, clarity and appeal of materials, delivery, and format.

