To **retain participants**, our team will gather robust details for tracking and tracing 1) at baseline, documenting multiple participant contact details and three individuals who know how to contact the family; 2) monthly contact via telephone or text; 3) follow up at least five times using different days, times, and methods. These strategies were successful in maintaining 100% retention at 1-month and 99% retention at 6-months in [name] and [name]' recent acceptability and feasibility trial with adolescents of the same age and setting for the parallel *Safe South Africa* trial.

Study timeline

Table 3. Study Timeline		Year 1			Year 2				Year 3				
3 month quarters		1	2	3	4	5	6	7	8	9	10	11	12
Development Phase (Aim 1)													
Translation and programming of school survey measures		✓											
Training of survey study team		✓											
Survey of school social ecology with students in the school community	✓	✓											
Survey of school social ecology with teachers in the school com-	✓	✓											
Analysis to draft poster campaign content and visuals			✓	✓									
Refinement Phase (Aim 2)													
Draft poster campaign content and finalize other intervention components				✓	✓	✓							
Translation of qualitative protocols							✓						
Training of qualitative interviewers and focus group facilitators							✓						
Focus group discussions with students								✓	✓				
Qualitative interviews with teachers								✓	✓				
Qualitative analysis to finalize intervention									✓	✓			
Refine poster campaign content and finalize other intervention components										✓			
Acceptability and Feasibility Phase – Pilot RCT (Aim 3)													
Interventionist training and supervision									✓	✓	✓		
Pilot RCT recruitment, eligibility screening, consent/assent, and baseline for boys and teachers								✓	✓	✓	✓		
1-month follow-up for boys									✓	✓			
6-month follow-ups for boys; teacher follow-up										✓	✓	✓	
Analysis of feasibility and acceptability data; analysis of outcome, mediation and moderation analysis												✓	
Manuscripts and Future Study Preparation													
Preparation of manuscripts						✓	✓	✓	✓	✓	✓	✓	✓
Preparation of follow-up grant applications											✓	✓	

Ethical Considerations related to the protection of human subjects

This research meets the definition of a clinical trial. This is not a Phase III clinical trial. We will seek IRB approval for all study procedures.

Risks to Human Subjects

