This research includes sensitive topics. Thus, there are some risks due to participation in our study. Concerns include risk of retribution against perpetrators disclosing in these studies. The risk of retribution against boys disclosing perpetration is guarded against by using self-completion for disclosure of acts that are socially stigmatizing or involve violence. The other concern is psychological distress; those who have raped or perpetrated sexual assault can find discussing it makes them realize that it was wrong. For consent and assent procedures, we will spend significant time discussing what topics will be covered, particularly highlighting what questions will explore including HIV-status, perpetration behaviors. We will emphasize that adolescents can halt participation at any time without consequence. We will also emphasize that although study staff will protect confidentiality of participants, this is not guaranteed in group settings. We also highlight the legal norms that would require break in confidentiality, and who information would be reported to as laid out by South African law. We balance these legal norms from South Africa on protecting the best interests of the child. For some data, we collect it anonymously (as in the school climate survey in Aim 1), participants will be guaranteed that the information will be kept confidential with no reporting given the anonymized data. In other cases of data for our other Aims, we follow the limits to confidentiality detailed above. Although our study protocol does not specifically probe for identifiable victims of perpetration, we recognize that there is the small chance adolescents will disclose this, unprompted by our team and requiring reporting. In anticipation of any possibility of serious adverse events, we will work with [name] and [name] affiliations with University of Cape Town's Department of Psychiatry to refer adolescents to appropriate HIV support, mental health, and social support services, via Groote Schuur and associated partner hospital and clinic services within South Africa's free public health service system. At the start of the study, we will establish a relationship with key officials in the Department of Social Development to ensure the appropriate referrals are made for at-risk adolescents and their families, and to facilitate the process of mandatory reporting of cases of child abuse. In addition, we will engage the services of a psychologist and social worker to ensure an effective referral system and mandatory reporting procedure. Furthermore, all adolescents (regardless of eligibility) will receive a list of resources of HIV, IPV, general health, and social services. We specifically promote access to information about Childline (for adults Lifeline), Stop GBV helpline, HIV helpline, FAMSA and the South African Depression and Anxiety Group (SADAG) helpline and dissemination of phone numbers to anyone who wants further support. In our weekly team meetings, we explicitly probe for any unanticipated ethical situations which do not need immediate emergency attention. All

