Adverse Events. If an unanticipated Problem or a Serious Adverse Event occurs at the study site and is more likely than not related to the research activity, and places participants or others at a greater risk of harm than was previously known or recognized, the M-PIs will report the event in writing using the appropriate forms to IRB. The M-PIs will also report Serious Adverse Events in writing to the sponsor. The M-PIs will review the Adverse Event report with the entire study team and gather any information needed to investigate the event and to determine subsequent action. The M-PIs will document and report any subsequent action to IRBs. We will also generate a brief report of Adverse Events for the study record each year, and we will forward the report to Brown University IRB, South African Medical Research Council IRB and NIH.

Potential Benefits of the Proposed Research to Human Subject and Others

There may be little or no direct benefit to participants from the study. Some possible benefits may include informing HIV and IPV prevention science. Adolescent participants will be given information on HIV, IPV, general health, and social services and referrals if necessary. The risks associated with this research are reasonable in relation to the anticipated benefits of advancing empirical knowledge adolescent prevention approaches for this high priority population and setting.

Importance of Knowledge to be gained

To our knowledge, this will be the first intervention to prevent adolescent HIV risk and IPV perpetration in an integrated manner and in a high impact setting (South Africa) using a school community-level approach.

Data and Safety Monitoring Plan:

The study population warrants the development of a Data Safety and Monitoring Plan including a Data and Safety Monitoring Board. To address the NIH policy for Data and Safety Monitoring, the M-PIs (Drs. [name] and [name]), along with the co-Investigator, will be responsible for monitoring ([name]). The team has developed a system for oversight of the proposed study and its participants. The Data and Safety Monitoring Plan focuses on protecting participants in the involvement in all three aims with primary data collection activities which occur in South Africa.

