
The Data and Safety Monitoring Plan for this application will begin by implementing standard procedures for day-to-day monitoring of the study. Also, we hold weekly meetings with the research team will be conducted to evaluate the progress of the trial and to review data quality, recruitment, study retention, and examine other factors that may affect safety. Participant experiences with the study procedures and the rates of adverse

events will also be reviewed to determine any changes in participant risk. The PI will report any adverse events (AEs) that are observed to the local site's IRB (South African Medical Research Council, Brown University, and to NIH. Serious adverse events (SAEs) will be reported to the local site's IRB by written report within 48 hours of our receipt of information regarding the event; SAEs will also be reported in writing to NIH. Actions taken by the IRB in response to SAEs will also be reported to NIH, as will reports of changes or amendments to the protocol as a result of an SAE. Reports of changes or amendments to the protocol in general must be requested first in writing to the IRB, which then will grant or deny permission to make the requested change or amendment in protocol. Modifications to study aims or design, if applicable as a response to SAEs, will also be submitted to NIH. Finally, if significant medical or mental health risks occur during the study period brought to the attention of the study team will be tracked as AEs; if significant medical or mental health risks occur during the study period that have a reasonable possibility of being related to the study will be referred for evaluation by the emergency department to determine whether hospitalization or urgent care is needed. In the event that a research participant either withdraws from the study or the investigator decides to discontinue a research participant due to SAE, the research participant will be monitored by the investigator via ongoing status assessment until either a resolution is reached (i.e. the problem requiring hospitalization has resolved or stabilized with no further changes expected or the SAE is determined to be clearly unrelated to the study intervention). Outcome of all SAEs will be periodically reported to NIH. A summary of the SAEs that occurred during the previous year will be included in the annual progress report to NIH.

Data and Safety Monitoring Board:

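### Adverse events are collected only when someone raises them: no described assessment asks participants about the named harms, so counts are likely to be low and have no denominator

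*Combined protocol and SAP*

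**What the plan says.** The sections on potential risks and on data and safety monitoring name two main risks. The first is retaliation: "Concerns include risk of retribution against perpetrators disclosing in these studies". The second is psychological distress in boys who are asked about, or who discuss, violence that they have committed.

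The rule for recording harms is in the Data and Safety Monitoring Plan. Significant medical or mental health risks "brought to the attention of the study team will be tracked as AEs", and "The PI will report any adverse events (AEs) that are observed to the local site's IRB". The same section says that the team will review adverse-event rates at its weekly meetings to see whether participant risk has changed. The DSMB is to review all adverse and serious adverse events and may recommend termination if significant risks develop.

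Scheduled data collection in both schools consists of "the outcome questionnaire used at baseline, 1- and 6-months for N=282 boys", plus a teacher survey at baseline and at the end of the school year. The retention plan adds "monthly contact via telephone or text", with no restriction by school.

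On-site activity during the trial differs by school. In School #2, Step 6 says: "Intercept activities will take place during 3 visits, facilitated by our team". Table 1 gives School #2 the teacher training and workbook, with School #3 as wait list, and adds: "Team provides ongoing technical assistance to help teachers engage in activities around the campaign".

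**The concern.** A harm enters the record only if someone sees it or volunteers it. Retaliation and distress among adolescents answering questions about sexual violence are events that many would not raise unprompted. Two things follow.

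- **Under-counting and no denominator.** A rate needs a known number of people who were asked. Under unsolicited capture, a low or zero count cannot be told apart from silence, yet the team and the DSMB are expected to judge participant risk from these counts.
- **Unequal opportunity to report.** Staff are on site between assessments in School #2 but not in School #3. If the DSMB looks at adverse events by school, part of any difference may reflect who had a study worker nearby to tell.

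This is a pilot in minors that is meant to prepare a larger trial. Whether harms can be captured reliably is something that it should find out.

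**Working it through.** The plan states no harm rate and no harms analysis, so there is no figure of its own to reproduce. The check has three parts.

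**1. Does any described instrument ask about harm?**

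- Table 2, boys: HIV risk, perpetration, bystander measures, covariates, mechanisms and moderators. It has no harm item. The depression scale is listed among the mechanisms and moderators at baseline, 1 and 6 months. It measures mood, but no rule turns a score or a change into an adverse event.
- Table 2, teachers: helping, bystander and norms measures, plus satisfaction. No harm item.
- Exit questionnaires (Aim 3 research material): reasons for dropping out, perceived burden, and satisfaction with the research team. Burden is the nearest to harm, but it covers neither retribution nor distress.
- Satisfaction forms: opinions on content, delivery and format, completed in School #2 only.
- Weekly probing for unanticipated ethical situations: done in team meetings, so it is put to staff, not participants.
- Monthly contact: listed as a retention measure, with no content on harms.
- Analysis section for Aim 3: no tabulation or analysis of harms.

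The instruments themselves are in Appendices L, M, O and P, which are not in the public text. The finding is therefore that nothing described asks about harm.

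**2. What would asking everyone provide?**

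For zero events among n people asked, the one-sided 95% upper bound on the reported rate is 1 − 0.05^(1/n), or roughly 3/n.

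- n = 141 (boys per school): 1 − 0.05^(1/141) = 0.0210, and 3/141 = 2.1%.
- With the plan's 3% dropout, 141 × 0.97 ≈ 137, and 3/137 = 2.2%.

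This bounds reported harm in that school, and only if those boys all answer. For zero spontaneous reports the number asked is unknown, so no bound can be calculated.

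**3. Can the difference in detection between schools be sized?**

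Let q be the chance that a harm surfaces at any one contact. Over k contacts the chance of capture is 1 − (1 − q)^k. Assume equal true harm in both schools, 2 follow-up assessments in each, and 4 extra contacts in School #2 (3 intercept visits and 1 satisfaction form). The value of q, its equality across contacts, and six monthly contacts are all assumptions.

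| q | Ratio, School #2 to #3, if monthly contacts reveal nothing (k = 6 v 2) | Ratio if six monthly contacts count in full (k = 12 v 8) |
|---|---|---|
| 0.05 | 0.26/0.10 = 2.72 | 0.46/0.34 = 1.37 |
| 0.10 | 0.47/0.19 = 2.47 | 0.72/0.57 = 1.26 |
| 0.20 | 0.74/0.36 = 2.05 | 0.93/0.83 = 1.12 |
| 0.30 | 0.88/0.51 = 1.73 | 0.99/0.94 = 1.05 |

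(Ratios are from unrounded values.) Under this model the direction is the same throughout, but the ratio runs from 1.05 to 2.72 according to the assumptions alone. The documents do not say where in that range, or outside it, the trial would fall.

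**The case against.** The other side has real strength.

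- **Between assessments the team is in touch with both schools.** A reader might infer that it works only in the intervention school. The retention plan's monthly telephone or text contact contradicts that. What stands is narrower: on-site activity is confined to School #2, and the monthly contact is not said to ask about harms.
- **Reports need not start with staff.** A reader might take the rule to mean that harms count only when staff notice them. The wording also covers reports brought by boys, parents or teachers. The point is that none of them is systematically asked.
- **No comparison of harms by school is planned.** The DSMB reviews all events, and arm comparisons are barred from its open session. With one school per arm, a comparison could not separate intervention from school even with perfect capture. This stands, so comparability is a caution about how the counts may be read and not an error in a planned analysis.
- **The named risks come mainly from disclosure and from questions on perpetration**, and the boys' outcome questionnaire is scheduled identically in both schools. This weakens the argument about unequal detection. It leaves under-counting untouched.
- **There is a structured mood measure, and the appendices are unseen.** Both are true. The depression scale has no link to adverse-event recording, and the appendices might contain a harm item that the protocol does not describe.
- **Asking has consequences.** Aim 3 boys are identifiable, so answers about threats or conflict could trigger mandated reporting. This cost belongs in the decision.

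**Conclusion.** The concern holds in this form. Adverse-event capture as described is unsolicited, and no described assessment asks about retribution or distress as harms. Under-counting is therefore likely, and the rates due for review have no denominator of people asked. This is more than a missing detail, because the stated rule cannot support the safety judgements that the plan assigns to the team and the DSMB.

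Spontaneous counts may also not be comparable between schools, because on-site contact is greater in School #2. No size should be attached to that. A reader might infer that the plan would manufacture a marked excess of harms in the intervention school. The documents give no harm rate and no chance of detection, so they do not support any particular ratio, and any comparison by school is descriptive only.

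The conclusion rests on the visible text. If Appendices L and M already carry harm items, what remains is to describe them in the protocol and say how they will be tabulated.

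**What to change.** - Add the same few self-completed harm items to the boys' 1- and 6-month questionnaires and to the teacher follow-up, in both schools: threats or retaliation linked to the study, distress from study content, and conflict over the campaign. The last goes beyond the two named risks; word it so that it can be answered in a school that has not yet had the campaign.
- Optionally, use one brief identical prompt at the monthly contacts in both schools.
- Record the source of each report (questionnaire, monthly contact, staff observation, participant, parent or teacher).
- Tabulate solicited and spontaneous harms separately by school, with the number asked beside each solicited count, and label the table descriptive.
- State whether the depression scale has any role in adverse-event recording.
- Reconcile the reporting rules. The Adverse Events section reports to the IRB an event that "is more likely than not related to the research activity" and raises risk beyond what was known, while the Data and Safety Monitoring Plan reports any that are observed.

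The cost is a few items and one table, using questionnaires and visits that already exist. Some answers may trigger the plan's existing referral and mandated-reporting duties, so the consent and assent forms should cover the new items.
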